3.6.13 Dose data categorization

The defined daily dose (DDD) is the assumed average maintenance dose per day for a drug used for its main indication in adults.

The DDD is a unit of measurement and does not necessarily reflect the recommended or prescribed daily dose.

The oral antidiabetic and Liraglutide dose data will be categorised as <=DDD and >DDD for each drug.

For Liraglutide, as per WHO, DDD is 1.2 mg.

For Metformin, 1500 mg will be considered as DDD and doses will be categorised as <DDD and >=DDD.

Statistical Program. Specification		Date:	10 September 2019	Novo Nordisk
Trial ID: NN2211-4232	CONFIDENTIAL	Version:	1.0	
UTN: U1111-1170-7035	CONFIDENTIAL	Status:	Final	
EudraCT No: 2015-002417-29		Page:	24 of 42	

Values of DDD mentioned below are taken from WHO website. Please refer to https://www.whocc.no/ddd/definition_and_general_considera/ for more information.

Table 13Defined daily dose for oral antidiabetics

Type of OAD	ATC code	Name	DDD	Unit
Sulfonylureas	A10BB01	glibenclamide	7	mg
Sulfonylureas	A10BB02	chlorpropamide	0.375	g
Sulfonylureas	A10BB03	tolbutamide	1.5	g
Sulfonylureas	A10BB05	tolazamide	0.5	g
Sulfonylureas	A10BB07	glipizide	10	mg
Sulfonylureas	A10BB08	gliquidone	60	mg
Sulfonylureas	A10BB09	gliclazide	60	mg
Sulfonylureas	A10BB12	glimepiride	2	mg
Alpha glucosidase inhibitors	A10BF01	acarbose	0.3	g
Alpha glucosidase inhibitors	A10BF02	miglitol	0.3	g
Alpha glucosidase inhibitors	A10BF03	voglibose	0.6	mg
Thiazolidinediones	A10BG02	rosiglitazone	6	mg
Thiazolidinediones	A10BG03	pioglitazone AT	30	mg
Dipeptidyl peptidase 4 (DPP-4) inhibitors	A10BH01	sitagliptin	0.1	g
Dipeptidyl peptidase 4 (DPP-4) inhibitors	A10BH02	vildagliptin	0.1	g
Dipeptidyl peptidase 4 (DPP-4) inhibitors	A10BH03	saxagliptin	5	mg
Dipeptidyl peptidase 4 (DPP-4) inhibitors	A10BH04	alogliptin	25	mg
Dipeptidyl peptidase 4 (DPP-4) inhibitors	A10BH08	teneligliptin	20	mg
Dipeptidyl peptidase 4 (DPP-4) inhibitors	A10BH05	linagliptin	5	mg
Sodium-glucose co-transporter 2 (SGLT2) inhibitors	A10BK01	dapagliflozin	10	mg
Sodium-glucose co-transporter 2 (SGLT2) inhibitors	A10BK02	canagliflozin	0.2	g
Sodium-glucose co-transporter 2 (SGLT2) inhibitors	A10BK03	empagliflozin	17.5	mg
Other blood glucose lowering drugs, excl. insulins	A10BX02	repaglinide	4	mg
Other blood glucose lowering drugs, excl. insulins	A10BX03	nateglinide	0.36	g

CONFIDENTIAL

Date: Version: Status: Page:

4 Analysis data creation and processing issues

4.1 Split datasets

Datasets larger than 5GB should be split

4.2 Data dependencies

4.2.1 Execution order

The execution order of some data derivations is crucial. The following selected data derivation rules apply in the given order:

- Partial date/time imputation.
- Laboratory LLOQ/ULOQ conversion.
- Reference range indicators
- Define ANELFL based on
 - o Fasting status
 - Visit reallocation
 - o Re-test
 - Last observed value before or at first drug date carried forward to baseline
- Setting observation period record flags, and other period variables

In the datasets with a visit structure (BDS) there should only be one record per subject per visit per parameter after the data derivations at this time (for ANELFL='Y').

- Endpoints calculation: BMI, , hypoglycaemia etc.
- Trial specific endpoints calculation
- Calculate values for variables relative to baseline
- Imputations in relation to analyses, e.g. Last values carried forward

In case of several derivations for a given parameter at a given visit, the DTYPE will be the last derivation in the order above. The variable DDCOM will show all derivations for the given parameter and visit, as e.g. 'LOQHALF | LOCF from AVISITN=110'.

4.2.1.1 Execution order of datasets

For execution order of dataset, the below Table 14 shows the dependencies between datasets and the macros or functions applied to create the datasets.

- Data located in same batch are independent of each other.
- A batch depends on previous batches.

Table 14Dataset dependencies and execution order

Batch	Data set	Macros or functions applied to create data
	ADSL (version 1)	
	ADSLSF	
	ADHBA1C	• External NN library: GCMD.topic_cd_def
		• External metadata: ADM.plnd_flowch_item_coll
	ADLB	• External NN library: GCMD.topic_cd_def
		• External metadata: ADM.plnd_flowch_item_coll
	ADVS	• External NN library: GCMD.topic_cd_def
		• External metadata: ADM.plnd_flowch_item_coll
	ADEC	• External NN library: GCMD.topic_cd_def
		• External metadata: ADM.plnd_flowch_item_coll
	ADSL (version 2)	
	ADHBA1C	• External NN library: GCMD.topic_cd_def
		• External metadata: ADM.plnd_flowch_item_coll
	ADLB	• External NN library: GCMD.topic_cd_def
		• External metadata: ADM.plnd_flowch_item_coll
	ADVS	• External NN library: GCMD.topic_cd_def
		• External metadata: ADM.plnd_flowch_item_coll

Statistical Pr Trial ID: NY UTN: U111 EudraCT No	rogram. Specification N2211-4232 1-1170-7035 o: 2015-002417-29	CONFI	DENTIAL	Date: Version: Status: Page:	10 September 2019 1.0 Final 27 of 42	Novo Nordisk
	ADEC	•	External NN l External meta	ibrary: GCMD.t data: ADM.plnd	opic_cd_def _flowch_item_co	oll
	ADEX	•	External NN 1	ibrary: GCMD.t	opic_cd_def	
	ADAE					
	ADCM					
	ADMH					
	ADHYPO					
	ADHYPOEN	•	External NN 1	ibrary: GCMD.t	opic_cd_def	
	ADTRTEV					
	ADTRTVIS	٠	External meta	data: ADM.plnd	_flowch_item_co	oll
	AXNR					
	ADRESP	٠	External NN 1	ibrary: GCMD.t	opic_cd_def	
	ADTTE	•	External NN 1	ibrary: GCMD.t	opic_cd_def	

4.3 Intermediate datasets

4.3.1 AXNR – Normal ranges lab data

Dataset containing normal ranges from the laboratory, that can be obtained from the central NN library GCMD.lab_range where lab='4232_ICON'. Normal range data will be applied in ADLB and listings.

Reference ranges for all the parameters in converted units is obtained using the SDTMMAP.SDTM_UNIT_CONVERSION dataset.

All lab parameters are identified from lab variable 'quest' uniquely corresponding to topic code and the dataset will add-on the ADaM analysis parameter variables PARAMCD, PARAM, and PARCAT1 obtained from the central NN library GCMD.topic_cd_def (see section 3.3 for definition of the variables).

CONFIDENTIAL

Date: Version: Status: Page:

4.3.2 ADTRTEV – Planned or actual treatment for events

ADTRTEV contains start and end dates for the events. It is based on the dataset SDTM.SE.

4.3.3 ADTRTVIS – Planned or actual treatment for findings

ADTRTVIS contains all the scheduled visits with start and end date and it is based on the SDTM.SV.

CONFIDENTIAL

Date: Version: Status: Page:

5 Analysis datasets descriptions

5.1 Overview

The ADAM datasets support all the statistical analyses of the efficacy and safety specified in the protocol and SPS. They are structured such that the statistical analyses can be performed with minimal programming. ADAM datasets are not generated specifically for outputs such as listings and other non-analytical displays.

5.2 Analysis Datasets

5.2.1 ADSL – Subject Level Analysis

The ADSL contains data from all randomised subjects, and the data will support all analyses, baseline characteristics, and disposition analyses. Data is built from SDTM DM and DS including also information from SUPPDM, SUPPSU, MH, SUPPMH, SV, CM, and EC.

ADSL data is built in two steps (batch 1 and 3 in Table 14). First version builds the ADSL data without baseline variables of HbA1c, FPG, BMI, weight, systolic blood pressure and diastolic blood pressure. Second step of ADSL add-on the listed baseline variables from lab (HbA1C and FPG) and vital sign assessments. Only the baseline variables in standard units is added to ADSL.

In the ADSL the date of randomisation is set to the date of visit 2, and not the randomisation date from IWRS. This has been chosen as there are some subjects with a randomisation visit (visit 2) date different from the randomisation date in IWRS.

5.2.2 ADSLSF – Subject level screening failures

The ADSLSF contains data from subjects not randomised (screening failure subjects in SDTM.DM) and reason for not being randomised.

Information from inclusion/exclusion SDTM data (SDTM.IE) is transposed and in case of multiple records per subject concatenated into an inclusion variable and an exclusion variable.

ADSLSF is the only dataset including subjects not enrolled.

5.2.3 ADAE – Adverse events analysis

ADAE contains all reported events for randomised subjects. All events from the first trial-related activity after the subject has signed the informed consent until the end of the post-treatment follow-up period are included. Data is built on SDTM data AE, SUPPAE, RELREC, and information from ADSL.

CONFIDENTIAL

Date: Version: Status: Page:

5.2.4 ADCM - Concomitant medication analysis

The ADCM contains all collected concomitant medication observations in SDTM.CM from randomised subjects. Information from SDTM.SUPPCM and SDTM.TS is added.

The continuation flag (CONTINFL) indicating if the concomitant medication is ongoing or not, relative to the treatment period, is set as "Y" when CM.CMENRF is equal to "ONGOING" otherwise it is set to blank.

The status relative to screening date (ASCRF) is set as "COMPLETED BEFORE" when analysis start date (ASTDT) and analysis end date (AENDT) is less than the screening date. ASCRF is set as "STARTED AFTER" when ASTDT is greater than the screening date. Finally, ASCRF is set as "ONGOING" when ASTDT is less or equal to the screening date and AENDT is greater or equal to the screening date or missing.

The status relative to baseline (ABLRF) is set as "COMPLETED BEFORE" when analysis start date (ASTDT) and analysis end date (AENDT) is less than the randomisation date (ADSL.RANDDT). ABLRF is set as "STARTED AFTER" when ASTDT is greater than the randomisation date. Finally, ABLRF is set as "ONGOING" when ASTDT is less or equal to the randomisation date and AENDT is greater than or equal to the randomisation date.

When AENDT is greater than or equal to the last visit date, ACRF or ABLRF is set to "ONGOING" based on ASTDT and AENDT is set to missing.

5.2.5 ADEX -- Exposure analysis set

The ADEX contains data of exposure to trial product for all randomised subjects. Data is built on SDTM.EX. There is an observation for each new dose for each subject.

5.2.6 ADEC -- Exposure analysis set

The ADEC contains data of exposure to trial product for all randomised subjects. Data is built on SDTM.EC and information from SDTM.SUPPEC is added. There is an observation for each new dose for each subject at each visit.

5.2.7 ADHBA1C – HbA1c

The ADHBA1C contains data for HbA1c assessments for all randomised subjects. Converted lab assessments also included in this dataset, see Appendix C.

The ADHBA1C is built in two steps and based on the SDTM datasets LB, and XL where LBTESTCD = "HBA1C", and add information from SUPPLB, AXNR, and ADBR. First version builds the complete ADHBA1C without the core efficacy and safety baseline variables. The second

Statistical Program. Specification
Trial ID: NN2211-4232
UTN: U1111-1170-7035
EudraCT No: 2015-002417-29

version depends on the completed ADSL dataset and add-on the efficacy and safety core baseline variables.

Date: Version:

Status: Page:

5.2.8 ADHYPO – Hypoglycaemic episode analysis

The ADHYPO contains data on all reported hypoglycaemic episodes for randomised subjects. All events from the first trial-related activity after the subject has signed the informed consent until the end of the post-treatment follow-up period are included. Data is built on SDTM data XH, SUPPXH, RELREC, and information from ADSL.

The ONTRTFL defines the on-treatment period for hypoglycaemic episodes as described in section 2.3.3. The TRTEMFL defined the on-treatment period with an addition of 1 more day (section 3.6.5).

The variables ACAT1 contains the analysis category 1 of ADA hypoglycaemic classification described in protocol. Each of the ADA classification categories are also marked in the variable flags ADASYMFL, ADDOCSFL, ADPROBFL, ADPSEUFL, ADSEVFL, ADUNCLFL, ADUNNSFL.

The variables ACAT2 contains the analysis category 1 of NN hypoglycaemic classification described in protocol. Each of the NN classification categories and merged categories are also marked in the variable flags NNASCOFL, NNCONFL, NNSECOFL, NNSEVFL, NNSYCOFL, NNSYSEFL, NNUNCLFL.

The date-time imputations follow the derivation rules in 3.6.1, and note that missing time information imputed to 00:00 implies that the hypoglycaemic episodes are imputed to occur during day-time.

5.2.9 ADHYPOEN – Hypoglycaemic episode analysis endpoint

The ADHYPOEN contains data on the number of treatment emergent severe hypoglycaemic episodes for all FAS subjects.

The counts are made over two periods: on-treatment or on-treatment+1 day, corresponding to ONTRFL='Y' and TRTEMFL='Y', respectively, in ADHYPO. This results in two rows per subject; one with the count for the on-treatment period with ONTRFL='Y' and TRTEMFL='' and one with the count for the on-treatment+1 day period with ONTRFL='' and TRTEMFL='Y'.

A binary variable indicating whether there are >0 or 0 episodes are also included using the CRIT1/CRIT1FL structure.

Statistical Program. Specification		Date:	10 September 2019	Novo Nordisk
UTN: U1111-1170-7035 EudraCT No: 2015-002417-29	CONFIDENTIAL	Version: Status: Page:	1.0 Final 32 of 42	

Endpoint	Topic code (PARAMCD)	Technical details
Severe hypoglycaemic	HYPO_N_TE_SEVERE	Sum of records with
episodes	(SEV_HYPO)	ADHYPO.ADSEVFL="Y"
		and
		ADHYPO.TRTEMFL="Y"
Severe or blood glucose	HYPO_N_TE_NNSBCFL	Sum of records with
confirmed symptomatic	(HYCNFSEX)	ADHYPO.NNSECOFL="Y"
hypoglycaemic episodes		and
		ADHYPO.TRTEMFL="Y"
Documented symptomatic	HYPO_N_TE_DOC_SYMP	Count of records where
hypoglycaemic episodes	(DOC_HYPO)	ADHYPO.TRTEMFL = "Y"
(ADA)		and ADHYPO.ACAT1 =
		"Documented symptomatic
		hypoglycaemia"

Table 15Derived hypoglycaemic endpoints

5.2.10 ADLB - Lab Analysis

The ADLB contains data for safety lab assessments for lipids, biochemistry, haematology, and pregnancy test, and the efficacy lab assessments for FPG for all randomised subjects. Converted lab assessments is also included in this dataset for a list of lab assessments which have been reported in multiple units, see PSPS Appendix 4.

The ADLB is built in two steps and based on the SDTM datasets LB, XL, SUPPLB, AXNR, and information from ADBR. Data for HbA1c measurements are excluded. First version builds the complete ADLB without the core efficacy and safety baseline variables. The second version depends on the completed ADSL dataset and add-on the efficacy and safety core baseline variables.

Parameters with character values are presented in AVALC and include topic codes of urine pregnancy test and information on whether urine or blood samples were collected. All other parameters are in nature numeric and their values are presented in AVAL. For numeric values truncated by a lower or upper limit of quantification the value in AVAL is derived as described in section 3.6.11. The SDTM variable LB.LBSTRESC is kept in ADLB for traceability of all values.

The analysis eligibility flag, ANELFL, is defined in accordance with rules described in section 3.5. The parameter , fasting plasma glucose is required to be assessed when the subject is fasting. For non-fasting subjects these assessments have ANELFL ='' (Section 3.6.10). All unscheduled (VISITNUM=29500) and non-visits (VISITNUM = 29999) have ANELFL = ''.

Statistical Program. SpecificationDate:Trial ID: NN2211-4232CONFIDENTIALVersion:UTN: U1111-1170-7035Status:Status:EudraCT No: 2015-002417-29Page:Page:	10 September 2019 1.0 Final 33 of 42	Novo Nordisk
--	---	--------------

In LB data LDL measurements calculated using Friedwald equation are reported with the topic code "CALC_LDL_CHOL_SERUM". If the triglycerides were >4.52 mmol/L, then the direct LDL cholesterol measurement is reported with topic code "LDL_CHOL_SERUM". In such cases a new row in entered in ADLB with CALC_LDL_CHOL_SERUM = LDL_CHOL_SERUM and dtype as derived.

5.2.11 ADMH – Medical History Analysis

The ADMH contain all general medical history and history of diabetic complications, from SDTM.MH for randomised subjects. Information from SDTM.SUPPMH is added.

The continuation flag (CONTINFL) indicating if the concomitant medication is ongoing or not, relative to the treatment period, is set as "Y" when CM.CMENRF is equal to "ONGOING" otherwise it is set to blank.

The medical analysis records (ANL01FL) is set to "Y" when (MH.MHOCCUR = 'Y' and MH.MHPRESP = 'Y') or when CONTINFL is non-missing. Otherwise the ANL01FL is empty, where the ANL01REA states "Does not meet criteria for analysis".

The status relative to screening date (ASCRF) is set as "COMPLETED BEFORE" when analysis start date (ASTDT) and analysis end date (AENDT) is less than the screening date. ASCRF is set as "STARTED AFTER" when ASTDT is greater than the screening date. Finally, ASCRF is set as "ONGOING" when ASTDT is less or equal to the screening date and AENDT is greater or equal to the screening date.

The status relative to baseline (ABLRF) is set as "COMPLETED BEFORE" when analysis start date (ASTDT) and analysis end date (AENDT) is less than the randomisation date (ADSL.RANDDT). ABLRF is set as "STARTED AFTER" when ASTDT is greater than the randomisation date. Finally, ABLRF is set as "ONGOING" when ASTDT is less or equal to the randomisation date and AENDT is greater than or equal to the randomisation date.

An illness is defined as a concomitant illness at screening if ASCRF is equal to either "ONGOING" or "STARTED AFTER". Similarly, an illness is a concomitant illness at baseline if ABLRF is equal to either "ONGOING" or "STARTED AFTER".

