8.2 Subject related information

8.2.1 Concomitant illness and medical history

A **concomitant illness** is any illness that is present at the start of the trial or found as a result of a screening procedure. **Medical history** is a medical event that the subject has experienced in the past.

Procedures and assessments performed at visit 1 and/or 2 are considered screening procedures. The results of these procedures should be considered pre-existing conditions and should be reported as medical history or concomitant illness

Relevant concomitant illness/medical history related to diabetes should be transcribed to the eCRF.

The information collected for concomitant illness/medical history should include diagnosis, date of onset and date of resolution or continuation, as applicable.

Any relevant change to a concomitant illness should be recorded during the trial. A clinically significant worsening of a concomitant illness must be reported as an AE, if the event meets the SAE criteria or is an AE leading to permanent treatment discontinuation according to section 12.2.

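### Three of the four ONGOING rules in the SAP (both in ADMH, the baseline rule in ADCM) need an end date that a continuing illness or drug does not have

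*SAP*

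**What the plan says.** SAP 5.2.4 (ADCM) and 5.2.11 (ADMH) each derive two status variables: ASCRF relative to the screening date and ABLRF relative to the randomisation date. All four rules call a record COMPLETED BEFORE if its start and end dates both precede the reference date, and STARTED AFTER if its start date follows it. They differ on ONGOING:

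- ADMH ASCRF: "when ASTDT is less or equal to the screening date and AENDT is greater or equal to the screening date".
- ADMH ABLRF: "when ASTDT is less or equal to the randomisation date and AENDT is greater than or equal to the randomisation date".
- ADCM ASCRF: the start date is on or before screening and "AENDT is greater or equal to the screening date or missing".
- ADCM ABLRF: the start date is on or before randomisation and "AENDT is greater than or equal to the randomisation date".

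ADCM has a further rule, which applies "When AENDT is greater than or equal to the last visit date": the status becomes ONGOING and the end date is then set to missing.

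ADMH uses the status as a definition. "An illness is defined as a concomitant illness at screening if ASCRF is equal to either" ONGOING or STARTED AFTER, and the same wording applies at baseline through ABLRF. The protocol, section 8.2.1, says that a concomitant illness "is any illness that is present at the start of the trial or found as a result of a screening procedure"; Amendment 1 revises other parts of that section but not this definition.

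The ADMH continuation flag CONTINFL is described as "indicating if the concomitant medication is ongoing or not, relative to the treatment period" and is set from CM.CMENRF. The selection flag ANL01FL is Y for a pre-specified term that occurred, or when CONTINFL is non-missing.

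**The concern.** A continuing condition is the plainest case of a concomitant illness, yet it is the case with no end date. A rule that compares the end date with a reference date, and says nothing about a missing one, cannot class such a record as ONGOING. In ADMH this reaches beyond a label, because the SAP's definition of concomitant illness rests on it. In ADCM the baseline status fails for drugs that simply continue, and the protocol requires background metformin to be maintained through the treatment period unless there is a safety concern.

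These variables describe the population at entry and help a reader judge whether the arms are comparable. An error here would tend to remove current conditions and keep past ones.

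**Working it through.** There is no sample size or power figure to reproduce. The check sets the rules against the data they will meet.

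**1. Does a continuing record have an end date?** Protocol 8.2.1 collects a resolution date or continuation for an illness, and 8.2.2 collects a stop date or continuation for a drug. SAP Table 8 imputes a stop date for both only when continuing is No. So AENDT is missing for a continuing record.

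**2. Apply the four rules as written.** With reference date R:

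- COMPLETED BEFORE: ASTDT < R and AENDT < R
- STARTED AFTER: ASTDT > R
- ONGOING: ASTDT ≤ R and AENDT ≥ R (ADCM ASCRF alone adds: or AENDT missing)

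The test records all start on day −400. Screening is day −14, randomisation day 0 and last visit day 728 (104 × 7). The SAP does not say how a comparison with a missing date behaves, so both possibilities are shown. The tests run in the order in which the SAP lists them.

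| Record | ADMH ASCRF | ADMH ABLRF | ADCM ASCRF | ADCM ABLRF |
|---|---|---|---|---|
| Continuing, comparison with missing is false | blank | blank | ONGOING | blank |
| Continuing, missing sorts below every date | COMPLETED BEFORE | COMPLETED BEFORE | COMPLETED BEFORE | COMPLETED BEFORE |
| Ended day 100 | ONGOING | ONGOING | ONGOING | ONGOING |
| Ended day 728 | ONGOING | ONGOING | ONGOING | ONGOING |
| Ended day −100 | COMPLETED BEFORE | COMPLETED BEFORE | COMPLETED BEFORE | COMPLETED BEFORE |

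Records with an end date are classed correctly throughout. In three of the four variables a continuing record is not ONGOING under either treatment of missing values. The fourth, ADCM ASCRF, is right unless missing sorts low and the COMPLETED BEFORE test runs first.

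**3. Does another rule rescue it?** The ADCM last-visit override needs an end date on or after the last visit, so it does not catch a record that never had one. It does set AENDT to missing for drugs already judged ongoing. If the status were derived after that step, those drugs would fall into the same gap.

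**4. Does CONTINFL rescue it?** In ADCM it marks continuing drugs whatever their end date, so the information survives there. In ADMH the definition repeats the ADCM one and reads a concomitant medication variable, although ADMH is built from SDTM.MH and SUPPMH. If that variable is not available, a continuing illness that is not pre-specified gets a blank CONTINFL and drops out through ANL01FL. If it is merged in by subject, illnesses could be selected because a drug is ongoing.

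**5. With the corrected rules,** a continuing record that started on or before the reference date is ONGOING in all four variables and meets the SAP's definition of concomitant illness.

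**The case against.** The strongest reply is that no output is shown to be wrong. The table shells are separate documents (Appendix A), SAP section 8 refers output to the project-level specification (PSPS), and protocol section 17 plans no analysis of concomitant illness or medication. A reader might infer that the trial's tables will leave out current conditions and drugs. The documents do not support that, because no supplied table is shown to select on ASCRF or ABLRF. This part of the reply stands.

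A reader might also infer that metformin is misclassified in all 1,994 subjects. That is the planned number to be randomised, and the inference assumes that every metformin record is open-ended. Protocol 5.4 allows a change for safety and 8.3.5 has diaries record metformin dose changes. A record closed after randomisation has an end date and is classed correctly. Metformin is also captured as diabetes treatment history (8.2.4) and has its own dose categories (SAP 3.6.13).

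Nor can both datasets be condemned as a whole, since the ADCM screening rule covers the missing end date. COMPLETED BEFORE is a conditional result: the SAP names SAS 9.4 but does not state how missing dates are compared or in what order the tests are coded.

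Two replies carry less weight. The PSPS might hold a general rule for missing end dates, but SAP 1.1 says that this document records deviations from it and additions to it, and the explicit rules here point to no such provision. The CM.CMENRF reference does look like a copying slip that a programmer would notice, but a silent correction would leave specification and dataset in disagreement.

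**Conclusion.** The point holds for three variables: ADMH ASCRF, ADMH ABLRF and ADCM ABLRF. As written, a continuing record cannot be ONGOING in any of them, and an illness that began before screening and still continues fails the SAP's definition of concomitant illness at both screening and baseline. The ADCM screening rule shows that the other three are probably an oversight. The ADMH continuation flag is a separate error, with a possible effect in either direction on which illnesses are selected.

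The number of records affected cannot be derived from the documents. The effect is limited to derived variables that describe concomitant illness and medication; neither the primary endpoint nor any secondary endpoint uses them. The conclusion assumes that continuing records carry no end date, as the data collection and Table 8 imply, and that no unseen PSPS rule overrides the text. It is worth correcting, but it does not threaten the trial's conclusions.

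**What to change.** - In SAP 5.2.11 (ASCRF and ABLRF) and 5.2.4 (ABLRF), let ONGOING also apply when AENDT is missing, as the ADCM screening rule already does.
- In all four rules, require a non-missing AENDT for COMPLETED BEFORE, so that the result does not depend on how missing values sort.
- In 5.2.4, state that the last-visit override is applied after the status has been assigned.
- In 5.2.11, derive CONTINFL from the medical history continuation variable instead of CM.CMENRF, and reword its description to refer to illness.

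That is 3 + 4 + 1 + 1 = 9 short edits, followed by a rerun of ADMH, ADCM and any output that reads these variables. No new data are needed.

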This trial will be conducted in a primary care environment which is defined as a nonendocrinologist, non-diabetologist clinic/practice/surgery or equivalent that provides continuing care to persons with any undiagnosed sign, symptom or health concern not limited by problem origin (biological, behavioural or social), organ system or diagnosis. The primary care practice may be the patient's first point of contact with the health care system.

The doctors/physicians that work in primary care are often referred to as general practitioners (GPs), primary care doctors/physicians and family doctors/physicians. The primary care practice may include a team of physicians and other health care professionals.

The definition of primary care is adapted from the definition used by the American Academy of Family Physicians $(AAFP)^{\underline{1}}$.

Assessments:

- HbA_{1c}
- Fasting plasma glucose
- Body weight
- Hypoglycaemic episodes

Trial products:

Victoza[®]:

• Victoza[®] (liraglutide 3.0 mL;6.0 mg/mL)

CONFIDENTIAL

Date: Version: Status: Page:

Oral antidiabetic drugs (OADs):

- Alpha-glucosidase inhibitors
- DPP-4 inhibitors
- Meglitinides
- SGLT-2 inhibitors
- Sulphonylureas
- Thiazolidinediones

Protocol	UTN: U1111-1170-7035	Date:	04 September 2015	Status:	Final	Novo Nordisk
Trial ID: NN2211-4232	EudraCT no.: 2015-002417-29	Version:	1.0	Page:	10 of 67	I

2 Flow chart

Trial Periods	Screening ¹	Random isation					Trea	tment				End of treatment	Follow up
Visit type	S	S	P/S^2	S	S	S	S	S	S	S	S	S	Р
Visit number	1	2	3	4	5	6	7	8	9	10	11	12	13
Timing of visit, Weeks	Up to -2	0	2	4	16	26	38	52	65	78	91	104	105
Visit window, Days			±7	±4	±10	±10	±10	±10	±10	±10	±10	±4	+4
Informed consent	х												
In/exclusion criteria	х												
Randomisation		х											
IWRS session	х	Х											
Withdrawal criteria ³			х	х	х	х	х	х	х	х	х	х	
Medical history /Concomitant illness	Х												
Concomitant medication	х	х	х	х	х	х	х	х	х	х	х	х	х
Demography	х												
Diagnosis of diabetes	х												
Diabetes complications	х							х				х	
Diabetes treatment history	х												
Smoking status	х												
Pregnancy urine test	х	(x)	(x)	(x)	(x)	(x)	(x)	(x)	(x)	(x)	(x)	х	
Handout ID card	х												
Height		Х											
Body weight		Х		х	х	х	х	х	х	Х	х	х	
Blood sampling		х		х	х	х	х	х	х	х	х	х	
- Fasting plasma glucose		Х		х		х		х				х	
- HbA _{1c}		х			х	х	х	х	х	х	х	х	
- Lipids		Х						х				х	
- Biochemistry		х						х				х	
- Haematology		х						х				х	

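### SAP 5.2.11 counts an illness that began after randomisation, with no time limit, as a concomitant illness at baseline

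*SAP*

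**What the plan says.** SAP 5.2.11 gives each medical history record a status relative to baseline, ABLRF, with three values: `COMPLETED BEFORE`, `STARTED AFTER` and `ONGOING`. The middle one is defined by onset alone: "ABLRF is set as 'STARTED AFTER' when ASTDT is greater than the randomisation date". The classification then follows: "an illness is a concomitant illness at baseline if ABLRF is equal to either 'ONGOING' or 'STARTED AFTER". A parallel rule uses ASCRF and the screening date to define concomitant illness at screening.

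The reference date comes from SAP 5.2.1: "In the ADSL the date of randomisation is set to the date of visit 2, and not the randomisation date from IWRS".

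On content, SAP 5.2.11 says: "The ADMH contain all general medical history and history of diabetic complications, from SDTM.MH for randomised subjects". Records are selected for analysis as follows: "The medical analysis records (ANL01FL) is set to 'Y' when (MH.MHOCCUR = 'Y' and MH.MHPRESP = 'Y') or when CONTINFL is non-missing". Neither statement limits records by visit or date.

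Protocol 8.2.1 defines a concomitant illness as "any illness that is present at the start of the trial or found as a result of a screening procedure", and treats visit 1 and visit 2 procedures as the screening procedures. Amendment 1 rewords other parts of that section but leaves this definition alone. The row "Diabetes complications" in the flow chart (Protocol section 2) is marked at visits 1, 8 and 12, that is, at screening, week 52 and week 104.

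**The concern.** A baseline characteristic should describe the subject before treatment could have had any influence. Under the SAP rule, an illness whose onset is strictly after the randomisation visit carries the baseline label, however late it began.

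Including `STARTED AFTER` makes sense for the screening definition, because up to two weeks separate visits 1 and 2 and an illness may appear between them. The SAP carries the same wording over to baseline, where the reference date is visit 2 itself and that reason no longer applies.

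Two features of the trial make this more than a wording matter.

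- **Collection after baseline.** Complications are collected again at weeks 52 and 104. Protocol 12.2 requires only SAEs, medical events of special interest and AEs leading to permanent discontinuation to be reported as AEs. A new non-serious complication outside those groups may therefore be recorded only at these two visits.
- **Unequal follow-up.** Amendment 1, section 2.11, implies different follow-up by arm. With 1994 / 2 = 997 subjects per arm, expected completers are 997 − 200 − 526 = 271 on Victoza and 997 − 200 − 606 = 191 on OAD (total 462, as stated). Longer follow-up gives more opportunity for a later-onset record, so the flag could differ between arms for reasons unrelated to baseline.

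**Working it through.** The plan gives no figure to reproduce, so the check is a literal application of the ABLRF rule.

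**Rule as written**, with S = start date, E = end date and R = randomisation date (visit 2):

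- S < R and E < R: `COMPLETED BEFORE`
- S > R: `STARTED AFTER`
- S ≤ R and E ≥ R: `ONGOING`
- Concomitant at baseline if `ONGOING` or `STARTED AFTER`

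**Test records**, all hypothetical, with R assumed to be 1 March 2017. Partial start dates are imputed to 1 January, as in SAP Table 8. The last column allows `ONGOING` to include a missing end date and excludes `STARTED AFTER`.

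| Record | ABLRF | SAP rule | `ONGOING` only | `ONGOING`, end date may be missing |
|---|---|---|---|---|
| 1 Jan 2010 to 1 Jan 2012 | `COMPLETED BEFORE` | no | no | no |
| 1 May 2015 to 1 Sep 2017 | `ONGOING` | yes | yes | yes |
| 1 May 2015, continuing, no end date | none | no | no | yes |
| 6 Dec 2017 (week 40), continuing | `STARTED AFTER` | yes | no | no |
| 21 Nov 2018 (week 90), continuing | `STARTED AFTER` | yes | no | no |
| Onset known only as 2017, continuing | none | no | no | yes |
| Onset known only as 2018, continuing | `STARTED AFTER` | yes | no | no |

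Three results follow.

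1. Illnesses beginning 40 and 90 weeks after randomisation are classed as baseline illnesses, which Protocol 8.2.1 does not allow.
2. An illness that began in 2015 and is still continuing without an end date is not classed as a baseline illness. The ADMH `ONGOING` rule needs an end date on or after randomisation, and Table 8 imputes a stop date only when the illness is marked as not continuing. The screening rule for concomitant medication in SAP 5.2.4 accepts a missing end date; the ADMH rules do not. Any repair has to deal with this too, because `ONGOING` would become the main criterion.
3. The rule works on onset date, not recording date. A complication first recorded at week 52 is caught only if its (possibly imputed) onset falls after visit 2.

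**The case against.** The strongest case on the other side has four parts.

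**Some later-dated findings do belong.** Visit 2 procedures count as screening procedures, and the first blood sample is taken at visit 2 and analysed centrally. A condition found from that sample may be dated after visit 2 and would still be concomitant under Protocol 8.2.1. This stands, and the remedy must keep such findings. It does not justify a rule without a cut-off. An illness found at visit 2 with onset on or before that day does not reach `STARTED AFTER` at all.

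**The route from weeks 52 and 104 to a baseline table is not shown.** A reader might infer that complications first recorded at those visits do enter the baseline summary. The documents do not support that. They do not say that the later entries are mapped to SDTM.MH or carry an onset date. Protocol 8.2.4 names visit 1 only, and Amendment 1, section 2.5, speaks of complications present at screening. The table shells listed in SAP Appendix A and the project-level specification, which might show whether a table selects on this class, are not available.

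**No endpoint analysis described uses this flag.** This stands. The primary test has no covariates, the ANCOVA uses treatment arm, country and the baseline value, and the SAP core variables contain no medical history.

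**Restricting to `ONGOING` would lose continuing illnesses.** The test records show that the existing rule already loses them when the end date is missing. The restriction does not cause the loss, but the repair should correct it.

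**Conclusion.** The point holds as a conflict between a stated SAP rule and the protocol's definition. Any ADMH record with onset after visit 2 is classed as a concomitant illness at baseline, without limit. Diabetes complications that begin on trial can be mislabelled in this way if the week 52 and 104 entries are in SDTM.MH with an onset date.

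The effect is limited to descriptive baseline data. Its size cannot be derived, because the documents give no incidence of new complications. Multiplying 1994 by an assumed incidence (2% gives about 40 subjects, 10% about 199) would be illustration only. It would also assume every link named above.

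Two further inferences should be resisted. The rule does not catch every on-trial complication, because a start date with a missing month is moved to January and can fall before randomisation. Nor are later-onset cases lost from the data: the start date and the `STARTED AFTER` value stay on the record. An arm difference through unequal follow-up is possible but not demonstrated. This is a minor but clear correction.

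**What to change.** Amend SAP 5.2.11 as follows:

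1. Remove `STARTED AFTER` from the definition of concomitant illness at baseline, except for findings of visit 1 or visit 2 procedures.
2. Extend both ADMH `ONGOING` rules (screening and baseline) to accept a missing end date for a continuing illness.
3. In the screening definition, limit `STARTED AFTER` to onset on or before visit 2, or to findings of visit 1 or 2 procedures.
4. Summarise complications with onset after randomisation separately by arm, as on-trial events.

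The SAP should also state which dataset holds the week 52 and week 104 complication entries and whether they carry an onset date, because item 4 depends on it.

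The cost is a few lines of specification, the matching program conditions and one extra descriptive summary. No visit or assessment needs to be added.
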